2. OBJECTIVES AND ENDPOINTS

The objectives and associated endpoints of this study are as follows:

Objectives	Associated Endpoints

 To evaluate the safety and tolerability of tapinarof cream, 1% in adults with plaque psoriasis 	
 Incidence, frequency, and nature of AEs and SAEs Change over time in clinical laboratory tests and frequency of clinically significant abnormal test results Change over time in vital signs and frequency of clinically significant abnormal results [REDACTED]

 To describe the efficacy of tapinarof cream, 1% over an extended period of time in adults with plaque psoriasis 	
 Proportion of subjects who experience a PGA ≥ 2 at least 1 time in the study and the median time from baseline to first worsening (PGA ≥ 2) for subjects entering the study with a PGA score of clear (0) Proportion of subjects who achieve a PGA score of 0 at least 1 time in the study [REDACTED] Duration of each treatment episode, defined as time from each treatment initiation/re-initiation to each subsequent treatment success (PGA score of 0). [REDACTED] Proportion of subjects who never achieve a PGA ≥ 2 throughout the study Proportion of subjects who never achieve a PGA score of 0 or 1 throughout the study [REDACTED] [REDACTED] Change and percent change from baseline in %BSA affected by visit (OC and LOCF) Change and percent change in PASI score by visit (OC and LOCF) [REDACTED]

 To describe the effect of tapinarof cream, 1% on psoriasis symptom severity and the associated impact on daily activities and attitudes in adults with plaque psoriasis 	
 Change in disease impact on daily activities, as measured by the Dermatology Life Quality Index (DLQI) total and individual dimension scores

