5.1.5. Administration of Study Drug

5.1.5.1. Treatment by Physician Global Assessment Score

Subjects entering with a PGA ≥ 1 will receive treatment with tapinarof cream, 1% until they achieve a PGA score of 0. If/when disease worsening occurs, as evidenced by a PGA ≥ 2 , treatment will then be re-initiated and continued until a PGA of 0 is observed. Subjects entering with a PGA of 0 will have treatment discontinued and be monitored for durability of response. If/when disease worsening occurs, as evidenced by a PGA ≥ 2 , treatment will then be re-initiated and continued until a PGA of 0 is observed. This treatment and re-treatment pattern of use will be continued until the end of the study (i.e., subjects may receive study treatment up until the Week 40 visit).

Subjects who experience suspected disease worsening between scheduled study visits may contact the study site to arrange an unscheduled visit (Section 7.5). See **Disease Worsening (PGA ≥ 2) During the Study** (Section 5.1.5.2) for further instructions. Upon confirmation of disease worsening, subjects will restart treatment with study drug.

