5.1.5.2. Disease Worsening (Physician Global Assessment Score ≥ 2) During the Study

If disease worsening is suspected between scheduled study visits, an unscheduled visit may be performed.

- If disease worsening (ie, PGA ≥ 2) is not confirmed, the subject will continue to be assessed at routine, scheduled visits (see Table 1).
- For each confirmed episode of disease worsening (ie, PGA ≥ 2) during the study (at either a scheduled or unscheduled visit), a treatment course of tapinarof cream (once daily) will be initiated and will continue until the subject achieves a PGA 0, as assessed at scheduled visits, approximately every 4 weeks (see Table 1).
- Subjects subsequently achieving a PGA of 0 will stop study drug and will then be assessed at routine, scheduled visits (see
- Table 1). Subjects who then experience suspected disease worsening between scheduled study visits may contact the study site to arrange an unscheduled visit (see
- Table 1).
 - If disease worsening is not confirmed, the subject will continue to be assessed at routine, scheduled visits.
 - If disease worsening is confirmed (ie, PGA ≥ 2) at either an unscheduled or a scheduled visit, subjects will initiate another treatment course of tapinarof cream (once daily) until a PGA 0 is achieved as described above.
- This treatment and re-treatment pattern of use will be continued until the end of the study (ie, subjects may receive study treatment up until the Week 40 visit).

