5.1.5.3. Application of Study Drug

Study drug will be dispensed to subjects requiring treatment at the study visits specified in the Schedule of Assessments (

[Table 1](#)).

Subjects will take the tubes home and self-administer (or have a caregiver apply if necessary), except on study visit days (when study drug is applied under supervision at the site), to affected areas once daily.

Subjects will be instructed to apply study drug as follows:

- For subjects with a PGA > 0, once daily application to affected areas including those areas treated in the pivotal study; subjects are to choose the application time they prefer and to apply the study drug at that time each day of study participation.
- Subjects with a PGA of 0 will not receive treatment but if they worsen and experience a PGA of ≥ 2 , apply once daily to newly affected areas only.
- If a subject misses a daily dose, it will be recorded as a protocol deviation. The subject should continue dosing the next day and should not apply more than once daily to make up for the missed dose on the previous day.
- If chosen application time is in the evening, the dose should be applied at least 30 minutes prior to bedtime.
- Study drug should be applied to dry, clean skin
- Wash hands after application, unless treating lesions on the hands or fingernails.
- Study drug should be applied to all lesions, including newly appearing lesions and lesions that have improved during the study.
- Subjects are allowed, but not required, to treat fingernails, toenails, palms, soles, and scalp lesions with study drug; however, efficacy analyses will not include assessment of improvement of psoriasis in these areas). If using study drug on the scalp, no other treatment for scalp psoriasis is permitted during the study.
- If there is residual cream visible on the disease-affected lesional skin, then the subject should be instructed to continue to lightly rub the cream into the skin until it is no longer visible
- If study drug is applied to the subject by another person, that person should thoroughly wash his/her hands after application. When possible, use of disposable gloves is recommended.
- Subjects should record the time of study drug application in the daily diary.
- Subjects should avoid swimming, bathing, showering, or strenuous activities for at least 2 hours after application of study drug.

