11.4 Study Medication Exposure and Compliance

Subjects will be characterized by a series of treatment episodes as defined in Section 11.7. These treatment episode definitions are based on attainment of specified PGA values.

The following exposure and compliance parameters will be summarized descriptively over the overall span of treatment episodes, overall and by DB treatment group:

- Total expected number of days exposed, calculated as the sum of number of days over all treatment episodes.
- Total number of doses administered within treatment episodes, calculated from the subject dose diary and summed over all treatment episodes. If a subject does not return diary or returns the diary with missing dosing record, the number of doses taken during that period is assumed to be 0.
- Grams (g) of study drug administered within treatment episodes, total will be summed over all treatment episodes. Drug administered is calculated as the summation of the difference between dispensed weight and returned weight for all returned tubes. Unreturned tubes will be assumed unused and will be included as 0 gram in amount drug used calculation. Average grams of study drug administered per expected day exposed and per doses administered will be calculated as the total grams / total number of days exposure (or total number of doses administered). Subjects with more than 1-day exposure but had no diaries returned will not have average grams per doses administered reported.
- Percent compliance will be calculated as the total number of doses administered within treatment episodes over the total expected number of days exposed.
- Subject compliance, defined as $\geq 80\%$ compliance over the entire duration of study. If the percentage of study medication compliance is unknown, the subject is assumed to be non-compliant with study medication.

In addition, the following exposure parameters will be summarized descriptively for the entire study (regardless of PGA status) overall and by DB treatment group:

- Total number of doses administered, calculated from the subject dose diary and in-clinic dosing. If a subject does not return diary or returns the diary with missing dosing record, the number of doses taken during that period is assumed to be 0.

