11.7 Efficacy Endpoints

Efficacy endpoints are as follows:

For subjects entering the study with a PGA score of clear (0):

- Proportion of subjects who experience PGA ≥ 2 at least 1 time during the study.
- Proportion of subjects who never experience PGA ≥ 2 throughout the study.
- Time to first worsening (PGA ≥ 2), defined as days from date of Visit 1 date to the date of first occurrence of PGA ≥ 2 . Subjects who never experience PGA ≥ 2 throughout the study will be censored at the date of their last PGA assessment.

For subjects entering the study with a PGA score ≥ 1 :

- Proportions of subjects who achieve PGA = 0 at least 1 time during the study

• [REDACTED]

• [REDACTED]

[REDACTED]

For subjects entering the study with a PGA score ≥ 2 :

- Proportions of subjects who achieved PGA = 0 or 1 at least 1 time during the study.
- Proportions of subjects who never achieve PGA = 0 or 1 throughout the study.

The following endpoints will be summarized over subjects in ITT population:

- Duration (days) of treatment episodes, defined as time (days) from the date of each PGA ≥ 2 (or PGA ≥ 1 for the first episode) to 1 day before each subsequent treatment success (PGA = 0). The date of the last PGA assessment will be used as the end date for episodes ongoing at the end of the study.

- [REDACTED]
- [REDACTED] \geq [REDACTED]
- [REDACTED]
- [REDACTED]
- [REDACTED]
- [REDACTED] change and percent change from baseline in %BSA affected by visit (OC and LOCF).
- [REDACTED] change and percent change from baseline in PASI score by visit (OC and LOCF)
- [REDACTED] \geq [REDACTED]
- [REDACTED] \geq [REDACTED]
- [REDACTED] \geq [REDACTED]

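### SAP 11.7 opens the first treatment episode at PGA ≥ 1 without limiting this to subjects who entered at PGA ≥ 1, so off-drug days at PGA 1 in subjects who entered clear can be counted as treatment

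*SAP*

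**What the plan says.** **Episode rule.** SAP 11.7 measures episode duration as "time (days) from the date of each PGA ≥ 2 (or PGA ≥ 1 for the first episode", ending the day before PGA 0. For an episode still open at the end: "The date of the last PGA assessment will be used as the end date for episodes ongoing at the end of the study". The bullet stands under the line "The following endpoints will be summarized over subjects in ITT population". SAP 11.8 names episode duration among the endpoints for Kaplan-Meier summary.

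**Protocol endpoint.** Protocol section 2 gives: "Duration of each treatment episode, defined as time from each treatment initiation/re-initiation to each subsequent treatment success (PGA score of 0". SAP section 12, which lists changes from the protocol, does not mention a different start.

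**Treatment of subjects who enter clear.** Protocol 5.1.5.1: "Subjects entering with a PGA of 0 will have treatment discontinued and be monitored for durability of response". Protocol 5.1.5.3: "Subjects with a PGA of 0 will not receive treatment but if they worsen and experience a PGA of ≥ 2", drug is then applied. Protocol 5.1.5.2 adds that if PGA ≥ 2 "is not confirmed, the subject will continue to be assessed at routine, scheduled visits". SAP section 3 describes the same pattern.

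**Use in exposure and compliance.** SAP 11.4 takes its episodes from 11.7 and defines: "Total expected number of days exposed, calculated as the sum of number of days over all treatment episodes". Percent compliance is doses within episodes divided by those days, and a subject is compliant at 80% or more. Unknown compliance is treated as non-compliance. Average grams per expected day uses the same denominator.

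**The concern.** The PGA ≥ 1 start suits a subject who enters at PGA ≥ 1 and begins drug at Visit 1. It does not suit a subject who enters clear. That subject can record PGA 1 at one or more visits with no drug dispensed, and the literal rule opens an episode at the first of those visits. If PGA returns to 0 without reaching 2, the result is a complete treatment episode during which no drug was applied.

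The SAP also conflicts with itself. For subjects entering at PGA 0, 11.7 counts time to first worsening from Visit 1 to PGA ≥ 2, so PGA 1 days are time not yet worsened. The episode rule counts the same days as treatment.

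Four summaries are at stake: the Kaplan-Meier episode duration, total expected days exposed, percent compliance with its 80% flag, and grams per expected day. Table 1 of the protocol (footnote j) gives out a diary only with drug, and SAP 11.4 scores a period without a diary as zero doses. Off-drug days therefore enter the compliance denominator and add nothing to the numerator.

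**Working it through.** The plan gives no figure on this point, so there is none to reproduce. The check applies the written rule to example PGA paths.

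**Inputs**
- Visits are every 28 days (Protocol 3.1), so Week w falls on Day 7w + 1. Weeks 8, 12, 16, 20, 24, 28, 36 and 40 are Days 57, 85, 113, 141, 169, 197, 253 and 281.
- Episode start as written: first PGA ≥ 1 for the first episode, PGA ≥ 2 for later ones. End: the day before PGA 0, or the last PGA (SAP 11.7).
- Drug start for PGA 0 entrants: PGA ≥ 2 (Protocol 5.1.5.1 to 5.1.5.3).
- Compliance = doses within episodes / episode days (SAP 11.4).

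**Assumptions.** The paths are hypothetical. Visits fall on target days, every dose due is taken and recorded, days are counted inclusively, and Week 40 is the last PGA.

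| Path | Episode days as written | Days on drug | Compliance as written |
|---|---|---|---|
| 1. Enters 0; PGA 1 at Week 8, 2 at Week 16, 0 at Week 28 | Days 57–196 = 140 | Days 113–196 = 84 | 84/140 = 60% |
| 2. As 1, but PGA 2 at Week 20 | Days 57–196 = 140 | Days 141–196 = 56 | 56/140 = 40% |
| 3. Enters 0; PGA 1 at Weeks 8 and 12, 0 from Week 16 | Days 57–112 = 56 | 0 | 0/56 = 0% |
| 4. Enters 0; PGA 1 from Week 8 to Week 40 | Days 57–281 = 225 | 0 | 0/225 = 0% |
| 5. As 3, then PGA 2 at Week 24, 0 at Week 36 | 56 + (Days 169–252 = 84) = 140 | 84 | 84/140 = 60% |
| 6. Enters 0; straight to PGA 2 at Week 8, 0 at Week 20 | Days 57–140 = 84 | 84 | 100% |
| 7. Enters 2; 0 at Week 12 | Days 1–84 = 84 | 84 | 100% |

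In path 1, Days 57 to 112 (56 days) lie both in the time before first worsening and in the treatment episode.

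**General form.** Let T be treated days over the whole study and u the untreated PGA 1 days that the rule adds. A fully adherent subject scores T/(T + u). This is below 0.80 when 0.20T < 0.80u, that is, when u > T/4. Grams per expected day shrinks by the same factor.
- u = 28: T = 56 gives 56/84 = 66.7%; T = 84 gives 84/112 = 75.0%; T = 112 gives 112/140 = 80.0%.
- u = 56: 80% needs T = 4 × 56 = 224.

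**With the first episode of PGA 0 entrants started at PGA ≥ 2.** Paths 1, 2 and 5 return to 100%. Paths 6 and 7 do not change. Paths 3 and 4 have no episode, so compliance is 0/0. Under the SAP 11.4 rule on unknown compliance they could still be flagged non-compliant, so the start date alone does not cure the flag for them.

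**The case against.** The strongest defence is that the authors meant only subjects who enter at PGA ≥ 1. SAP section 3 describes those subjects as treated from the start and PGA 0 entrants as re-treated at PGA ≥ 2. An interval without drug is not naturally a treatment episode. SAP section 1 says the plan adds detail to the protocol without repeating all its definitions, and the ITT line may only name the summary population. This may well be the intent, and a reader should not infer a deliberate choice to count untreated time. But 11.7 separates subjects by entry PGA for other endpoints and does not do so here, and 11.4 says that its episodes rest on attained PGA values. A programmer following the text would get the results above.

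The PGA > 0 bullet in Protocol 5.1.5.3, read alone, might suggest that an off-drug subject at PGA 1 is on treatment. The bullet after it, with 5.1.5.1 and 5.1.5.2, ties the restart to PGA ≥ 2.

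Three stronger readings are tempting and are not supported:
- *Off-drug clearing inflates the response rates.* The proportion reaching PGA 0 is limited to subjects entering at PGA ≥ 1, and time to first worsening uses PGA ≥ 2. Neither changes. Some neighbouring bullets are redacted, so nothing can be claimed about them.
- *The safety and exposure case is undermined.* The whole-study totals of doses and grams in 11.4 do not use episodes, nor does the adverse event incidence plan in 11.11.1. SAP section 9 does not say that its counts of subjects with 26 and 52 weeks of exposure come from expected days.
- *Subjects would be wrongly excluded.* ITT is the only analysis set, so the 80% flag removes nobody.

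It also stands that the study is descriptive, with no statistical testing.

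**Conclusion.** The point holds as a defect in the rule as written. The affected subjects enter at PGA 0 and record PGA 1 before PGA ≥ 2, or never reach PGA ≥ 2. For them, off-drug days lengthen or create treatment episodes, inflate expected exposure, and dilute compliance and grams per expected day. The effect on one subject can be large: 60% or 40% compliance with perfect dosing in paths 1 and 2, and 225 days of apparent exposure without drug in path 4. It can also be harmless to the flag: with u = 28 and T of at least 112, the subject stays at 80% or above.

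Direct moves from 0 to PGA ≥ 2, subjects entering at PGA ≥ 1, later episodes and the whole-study dose and gram totals are unaffected. The documents give neither the number of PGA 0 entrants nor their time at PGA 1, so no shift in the study median or compliance rate can be stated. The rule should be corrected before database lock. It does not threaten the main conclusions of the study.

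**What to change.** In SAP 11.7:
- For subjects entering at PGA ≥ 1, start the first episode at Visit 1.
- For subjects entering at PGA 0, and for all later episodes, start it on the date of the PGA ≥ 2 at which drug is re-initiated.
- State that PGA 1 while off drug opens no episode.

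This agrees with the protocol endpoint.

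In SAP 11.4, use the same dates. Leave subjects with zero expected days out of the percent-compliance and ≥ 80% summaries, and report their number, so that the rule on unknown compliance does not class them as non-compliant.

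The cost is a sentence or two in each section and a small change to the episode derivation. No new data are needed. Only the analysis definition changes, not any treatment rule.

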7.2. Visits 2 to 10; Treatment Period

Subjects entering with a PGA ≥ 1 will receive treatment with tapinarof cream, 1% until they achieve a PGA score of 0, at which time treatment will be discontinued and subjects monitored for durability of response. If/when disease worsening occurs, as evidenced by a PGA ≥ 2 , treatment will then be re-initiated and continued until a PGA of 0 is observed. Subjects entering with a PGA of 0 will have treatment discontinued and be monitored for durability of response. If/when disease worsening occurs, as evidenced by a PGA ≥ 2 , treatment will then be re-initiated and continued until a PGA of 0 is observed. Subjects will return to the study site at least every 4 weeks (± 3 Days) during the 40-week monitoring period. The following assessments will be performed:

- Brief physical exam
- Vital signs measurements
- Urine pregnancy test (females of CBP)
- Blood sample collection for clinical laboratory tests (serum chemistry, hematology, diagnostic tests); Weeks 4, 12 only
- Photography of a representative area of the subject's disease area (optional for subjects; at a subset of study centers)
- PGA score
- BSA affected calculation
- PASI
- LTS (if patient has been applying study drug for the treatment period prior to the scheduled visit)
- DLQI
- AE recording
- Concomitant medication recording
- Collect and dispense diary, if applicable (subjects will be instructed in how and when to complete diary)
- Review diary for treatment compliance, if applicable
- Dispense and collect study drug, if applicable
- Instruction on how to apply study drug, if applicable
- Study drug application under supervision, if applicable

7.3. Visit 11;

The following procedures and assessments will be performed at the Week 40 Visit:

- Brief physical exam
- Vital signs measurements

- Urine pregnancy test (females of CBP)
- Blood sample collection for clinical laboratory tests (serum chemistry, hematology, diagnostic tests)
- Urinalysis
- Photography of a representative area of the subject's disease area (optional for subjects; at a subset of study centers)
- PGA score
- BSA affected calculation
- PASI
- LTS (if patient has been applying study drug for the treatment period prior to the scheduled visit)
- DLQI
- Patient Satisfaction Questionnaire
- AE recording
- Concomitant medication recording
- Collect diary, if applicable
- Review diary for treatment compliance, if applicable
- Collect study drug, if applicable

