7.4. Follow-up Visit

Subjects will return to the study site 4 weeks (± 3 days) after last treatment to complete follow-up assessments as follows:

- Brief physical exam
- Vital signs measurements
- Urine pregnancy test (females of CBP)
- Blood sample collection for clinical laboratory tests (serum chemistry, hematology, diagnostic tests)
- Urinalysis
- Photography of a representative area of the subject's disease area (optional for subjects; at a subset of study centers)
- PGA score
- BSA affected calculation
- PASI
- DLQI
- AE recording
- Concomitant medication recording

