3. STUDY DESIGN

This is a long-term, open-label, multicenter, study to evaluate the safety and efficacy of topical tapinarof cream, 1% in adults with plaque psoriasis. Subjects in this study completed treatment with tapinarof or vehicle in 1 of 2 pivotal Phase 3 efficacy and safety studies (Study DMVT-505-3001 or Study DMVT-505-3002). The study consists of up to 40 weeks of treatment and a 4-week safety follow-up period.

At the completion of the Week-12 Visit of the pivotal study (Visit 1, Baseline [Day 1] in this study), eligibility of the subjects opting to enroll in this extension study is confirmed. Study visits during the treatment period occur every 4 weeks (± 3 days). A Phone Call is performed at Week 2 (Day 15). Unscheduled visits occur, as needed. Subjects who withdraw from the study before Week 40 return to the study center for an Early Termination Visit. The total duration of study participation is approximately 44 weeks.

At the start of the study, subjects entering with a PGA ≥ 1 receive treatment with tapinarof cream, 1% until they achieve a PGA score of 0, at which time treatment is discontinued and subjects are monitored for durability of response. If/when disease worsening occurs, as evidenced by a PGA ≥ 2 , treatment will then be re-initiated and continued until a PGA of 0 is observed.

Subjects entering with a PGA of 0 will have treatment discontinued and they will be monitored for durability of response. If/when disease worsening occurs, as evidenced by a PGA ≥ 2 , treatment is re-initiated and continued until a PGA of 0 is observed.

The pattern of treatment, suspension and re-treatment is continued until the Week 40 visit.

Study drug dispensed to subjects during the clinic visits is applied once daily to all affected areas, including newly appearing lesions and lesions that improve during the study. Subjects

apply sufficient study drug to cover completely each lesion with a thin layer of study drug and record the time of study drug application in a daily diary provided by the study site. Subjects may treat fingernails, toenails, palms, soles, and scalp lesions with study drug; however, improvement of psoriasis is not assessed in these areas.

Safety assessments include AEs, local (application site) tolerability, clinical laboratory tests, vital signs, physical examinations, and investigator-assessed LTS. Efficacy assessments include a 5-point static PGA (0-4 scale), %BSA affected, the PASI, and subject-reported DLQI.

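### SAP 11.7 closes an open treatment episode at the last PGA with no on-treatment limit, so about 28 days without drug can enter the compliance denominator of SAP 11.4

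*SAP*

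**What the plan says.** SAP 11.7 starts a treatment episode at a PGA of 2 or more (1 or more for the first episode) and ends it one day before the next PGA of 0. For episodes that have not closed, "The date of the last PGA assessment will be used as the end date for episodes ongoing at the end of the study".

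SAP 11.4 takes its episodes from 11.7 and builds three quantities on them:
- The denominator: "Total expected number of days exposed, calculated as the sum of number of days over all treatment episodes".
- Compliance: "Percent compliance will be calculated as the total number of doses administered within treatment episodes over the total expected number of days exposed". A subject counts as compliant at 80% or more.
- Rate of use: "Average grams of study drug administered per expected day exposed and per doses administered will be calculated as the total grams", divided by days or by doses.

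On when treatment stops, SAP 3 states: "The pattern of treatment, suspension and re-treatment is continued until the Week 40 visit". Protocol 5.1.5.2 says the same: "continued until the end of the study (ie, subjects may receive study treatment up until the Week 40 visit". Under Protocol 7.2, sites dispense and "collect study drug, if applicable" at Visits 2 to 10. The Week 40 list in Protocol 7.3 keeps the collection and has neither dispensing nor supervised application.

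Protocol 7.4 brings subjects back 4 weeks (±3 days) "after last treatment to complete follow-up assessments as follows", and PGA is on that list.

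**The concern.** The denominator is meant to count days on which a dose was expected. For a subject whose episode is open at Week 40 and who attends follow-up, the last PGA is the follow-up PGA. The four weeks before it are days on which the plan supplies no drug, yet the rule counts them. The error always has the same direction: percent compliance and grams per expected day come out too low and episode duration too long. Some subjects who missed no dose would be labelled non-compliant. The effect is largest for subjects with few treated days, which is a foreseeable pattern under intermittent treatment.

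A second case follows from the same wording. A PGA of 2 or more first seen at Week 40 opens an episode although no drug is dispensed at that visit.

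The visible text also does not say that the end date of an open episode is a censoring date, although SAP 11.8 sends episode duration to Kaplan-Meier. For time to first worsening, SAP 11.7 does say so.

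**Working it through.** **Gap.** Protocol Table 1 puts the Week 44 follow-up on Day 309, and 7 × 44 + 1 = 309 reproduces it. The same rule gives Week 40 as 7 × 40 + 1 = 281. The gap is 309 − 281 = 28 days, or 25 to 31 with the ±3-day window. It is 29 if both end dates are counted, and 27 (by simple date difference) if the follow-up PGA is 0, because the episode then ends a day earlier.

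**Numerator.** SAP 11.4 takes within-episode doses from the diary, and whole-study doses from the diary and in-clinic dosing. Whether supervised doses are in the compliance numerator is therefore unclear, and both readings are shown. Supervised doses fall at Visits 1 to 10, one per 28 treated days for an episode opened at a scheduled visit: 10 in 280 days.

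**Score of a subject who misses no dose over T treated days, last episode open at Week 40, 28-day gap:**

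| T | All doses counted: T/(T+28) | Diary doses only: (27T/28)/(T+28) |
|---|---|---|
| 280 | 280/308 = 90.9% | 270/308 = 87.7% |
| 168 | 168/196 = 85.7% | 162/196 = 82.7% |
| 112 | 112/140 = 80.0% | 108/140 = 77.1% |
| 84 | 84/112 = 75.0% | 81/112 = 72.3% |
| 28 | 28/56 = 50.0% | 27/56 = 48.2% |

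Over the visit window, the all-doses score is 280/311 = 90.0% to 280/305 = 91.8% at 280 days, and 84/115 = 73.0% to 84/109 = 77.1% at 84 days.

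**80% threshold.**
- All doses: T/(T+g) = 0.80 gives T = 4g. That is 112 days for g = 28, 100 to 124 over the window, 108 for g = 27 and 116 for g = 29. Since 281 − 169 = 112 and Week 24 is Day 169, a subject whose only episode opened after Week 24 and is still open at Week 40 fails with perfect adherence.
- Diary only: 27T/28 = 0.8(T+28) gives T = 627.2/4.6, about 136 days.
- True adherence of 90%, all doses: 0.9T/(T+28) = 0.80 gives T = 224 days.

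**Other quantities.**
- Grams per expected day is diluted by 28/(T+28): 28/308 = 9.1% at 280 days, 28/112 = 25% at 84.
- A first PGA of 2 or more at Week 40, with no earlier treatment, scores 0/28.
- Kaplan-Meier: for an episode open from Day 1, the censoring time moves from about day 280 to about day 308. The curve before then is unchanged.

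**Check of the remedy.** An episode running from Day 1 through Day 280, the day before Week 40, has 280 days counted inclusively. Full adherence gives 280/280 = 100% (270/280 = 96.4% if only diary doses are counted). A subject who doses daily for 140 days and then stops, with the episode still open, scores 140/308 = 45% as written, 140/280 = 50% with the Week 40 limit (the true adherence), and 140/140 = 100% if the episode is cut at the last dose.

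**The case against.** The strongest reply is that the end of the study, for a subject, means Week 40. Protocol 5.1.5.2 uses the phrase that way, and SAP 3 sets subject completion at Visit 11. Protocol 7.8 ties the phrase to the Week 44 follow-up, but as a trial-level milestone for the last active subject, so the two uses need not conflict. A programmer could reasonably close open episodes at Week 40. This stands as far as it goes: the text is open to a benign reading. But the phrase only selects which episodes count as ongoing. The end date is still the last PGA, with no limit.

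Three further objections stand and narrow the point:
- The figures depend on the numerator. T/(T+28) and the 112-day threshold hold only if in-clinic doses are counted.
- A reader might take the planned 300 completers of 850 as a ceiling on the subjects affected. The documents do not support that. Protocol 4.6.1 lets subjects taken off drug stay for safety assessments, Protocol 7.4 does not limit follow-up to completers, and Protocol 7.7 sets no interval between last dose and the early termination visit.
- A subject who enters with PGA of 1 or more and never clears has about 280 treated days and, if fully adherent, passes the 80% cut on either numerator.

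On Kaplan-Meier, censoring an unresolved episode is the natural reading of the product-limit method, and parts of SAP 11.7 are redacted. The missing statement calls for clarification and is not evidence of a biased curve.

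**Conclusion.** The rule as written gives a wrong denominator for an identifiable group: about 28 days without drug are counted as expected dosing days for a subject with an episode open at Week 40 who has a follow-up PGA. This should be fixed, but the consequence is limited. The study is descriptive with no testing, no analysis set depends on the compliance flag, and whole-study doses, total grams and grams per dose do not change. The harm is confined to the compliance, grams-per-expected-day and episode-duration tables, and the Kaplan-Meier effect is small.

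A reader might infer that mean compliance in the study will be materially understated. The documents do not allow that conclusion. They give neither the share of subjects with an open episode nor the distribution of treated days, so the effect on group means is unknown. The individual figures assume follow-up on schedule and the stated treatment of in-clinic doses.

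**What to change.** - **Exposure and compliance (SAP 11.4):** count expected dosing days of an open episode only through the day before the Week 40 visit, the early termination visit, or the recorded date of permanent study drug discontinuation, whichever is first. Do not cut at the last dose taken, because that removes non-adherent days from the denominator.
- **Late PGA findings:** add no expected days for a PGA first seen at Week 40 or at follow-up.
- **Episode duration (SAP 11.7 and 11.8):** state that an open episode is censored at the last on-treatment PGA in the Kaplan-Meier summary.
- **Consistency:** use the same dose source (diary with or without in-clinic doses) and the same day-counting convention in numerator and denominator.

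The cost is SAP wording and derivation code. Visit dates are already collected. SAP 11.1 already tabulates permanent withdrawal of drug, and the team should confirm that its date is in the database. Expected days fall by about four weeks per affected subject. No dosing or visit rule changes.
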